Metformin has been in use since 1957 but its specific mechanism of action is unknown (62). Previously, AMPK-activation has been identified as one of the mechanisms by which it exerts its angiogenic activity (63). However, metformin does not activate AMPK directly. Instead, AMPK activation is a result of metformin inhibition of the mitochondrial respiratory chain complex 1 (reviewed in (64,65)). Apart from diabetes, it has also been implicated in the prevention of cancer, adverse outcomes in women with PCOS and most recently in the prevention of PET (reviewed in (66)). In an ex-vivo study using primary placental tissue from PET placentas, metformin treatment resulted in reduced endothelial dysfunction, enhanced vasodilatation and induced angiogenesis by sFlt-1 and endoglin reduction possibly at the mitochondrial level (30). Despite these, the exact mechanism behind its role in the prevention of PET remains poorly understood. Further clarification of how metformin decreases the incidence of pre-eclampsia needs to be examined. Here we plan to explore altered maternal serum levels of sFlt-1, PIGF and VEGF in pregnant women using metformin.

5. Study design and methodology

This is an open label, randomized control trial (RCT) in which high risk for pre-eclampsia pregnant subjects will be randomly assigned to either an intervention group (metformin 1 gm twice daily plus aspirin 100 mg per day and standard of care) versus control group (aspirin 100 mg per day and standard of care) that will be administered between 11^{+0} to 13^{+6} weeks of gestation until delivery (appendix 1). Only women at high risk of pre-eclampsia as defined by the ACOG practice bulletin will be included (see inclusion criteria). Patient assignment will not be blinded as control group will not be given a placebo; the data will be analyzed on an intention to treat basis. Enrolled subjects will be followed throughout pregnancy and up to 30 days post-delivery (as per hospital practice).

Study definitions:

High risk of preeclampsia:

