Age under 18 years, hyperemesis gravidarum, unable to sign the consent form, type 1 or 2 diabetes mellitus, early gestational diabetes, auto-immune disease, fetal abnormality identified at time of scanning (between 11⁺⁰ and 13⁺⁶ weeks of gestation), bleeding disorder, peptic ulcer, hypersensitivity to aspirin or metformin, long use of NSAIDS before initiation of intervention, contraindication to metformin or aspirin and participation in another concurrent trial.

Study sites:

The study will be conducted at the Women Wellness and Research Center (WWRC), Doha, Qatar. Patient will be identified from three Primary Health Centers. There will, however, will be very few volunteers who will have all their visits and tests done at the WWRC with the health center facilitating their identification only.

Study methods:

Patient identification and randomization

If the primary physician in the Primary Health Center or the main center identifies a potential candidate for the study based on the inclusion and exclusion criteria, he/she will inform the patient about the study and document her willingness to participate in the study in the electronic medical record to avoid cold calling and according to HIPAA recommendations. The investigator of the respective site will then be contacted through email by the primary physician.

the patient will be contacted by the study investigator and arrange an appointment in the WWRC to inform her about the study and if she accepted to participate, give her the patient information leaflet (PIL) and then obtain informed consent once all her questions have been answered.

Each center has one coordinator, who will be responsible in conjunction with the investigator for recruitment, clinical interviews, determining eligibility and obtaining signed informed consent forms. After successful screening, eligible pregnant women will be randomly assigned to either intervention or control group. Random sized blocks of 4 or 6 will be computer generated with 1:2 ratio.

Sample isolation and laboratory studies (appendix 2):

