Randomization and initiation of the study:

Once recruited, the patient data will be entered onto a web-based randomization software to determine study group and to the clinical trial management software, where a study ID number will be assigned. If the patient agrees to enter the trial, the site coordinator will contact the study physician to initiate study protocol (appendix 2) and then the patient will continue to be followed-up by her clinical team. In cases where patient assigned to control group and diagnosed with GDM and started on metformin, she will be moved to intervention group and analyzed as late started. If patient declined to participate initially, or dropped out from the study, all her data will be removed.

A clinical trial management software will be utilized to enter patient data. Each study Co-PI (physician) will lead a study site and supported by study coordinator. They will be responsible for reviewing patient eligibility, initiating the study protocol and patient counselling. They will meet regularly to share study updates. Study coordinators will be responsible for patient counselling, obtaining written informed consent, data collection and entry, and blood samples and placenta shipment from the study sites to study research laboratory at Sidra Medicine. The LPI will meet with the research team monthly to review various aspects of the trial to ensure conformation to the protocol and principles of GCP.

Collected data (appendix 5):

Variables to be collected include patient demographic characteristics, past medical and surgical history, past medication history, allergies, vital signs, CBC as routinely done and LFT, serum creatinine and biomarker serum level (sFlt-1, VEGF, PIGF). Blood samples will be collected by the phlebotomist or the responsible nurse. The blood investigations, 5 ml blood sample will be collected at baseline, second and third trimester and after delivery. The blood sample will be used for CBC, LFT, serum creatinine, and study serum biomarker in aim 2 (sFLT-1, VEGF, PIGF), and well as for storage for future DNA/RNA analysis for aim 3. Further, placenta samples will be collected and stored for future DNA/RNA analysis.

Medication adherence and adverse drug related events (ADRs):

Medication adherence is crucial to achieve the study objectives. Patient medication adherence is measured using the pill count method on each visit and Morisky scale (appendix 6) in

1st - Revised On May 2017

Page 12 of 22

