each visit or telephone call. Furthermore, to increase patient medication adherence, a reminder SMS will be send as well as three telephone calls to individual patient on regular basis. Adverse drug reaction (ADRs) will be reported using [name] Medical Corporation ADR form (Appendix 7) to both DSMC and MRC when they occur, however, serious ADRs will be reported within 48 hours by the study PI.

6. Sample size and calculation

Our sample size calculation was based on Syngelaki A. et al. (2016) findings. In this study, obese patient where either randomized to metformin or placebo to see the effect on neonatal birth weight. As a secondary outcome, metformin use was associated with 76% reduction in PET (3% versus 11.3% respectively, OR 0.24, 95% CI 0.10 – 0.61, $P = 0.001$).

We expect that for a study power of 80% and to detect a reduction at a level of 5% significance, with considering above outcome estimates it is approximately estimated to be 172 patients in each arm, for a total of 344 in both group based on 1:1 ratio. Allowing for a maximum 20% dropout, we estimate that 414 patients would need to undergo randomization, to give 207 patients in each group.

7. Data collection methods and procedure

These will be at baseline, in the second and again in the third trimesters. The data to be collected include patient clinical information, blood sample and placental tissue (appendix 5). At each study visit 5 ml maternal venous whole blood will be collected by a laboratory phlebotomist or a nurse (one at baseline, and one at each following trimester/visit and admission/s, see appendix 2) for all included subjects. The blood sample will be used for measuring blood markers for aim 2 and stored for future DNA/RNA analysis for aim 3. In addition, placental tissue will be collected and stored for future DNA/RNA analysis. In brief:

- (a) Baseline Data (Week 11⁺⁰ to 13⁺⁶): Patient sociodemographic data including age and ethnicity, Obstetrical, medical, surgical and medication history, current pregnancy information, CBC, as routinely done and study biomarkers of LFT, serum creatinine, sFlt-1, VEGF and PIGF.
- (b) Second (week 19⁺⁰ to 24⁺⁶) and third trimester visits (week 32⁺⁰ to 34⁺⁶): At these visits the same data collected at baseline will be obtained. If the patient is, however, admitted for pre-eclampsia before the third visit, the collection will follow the pre-eclampsia diagnosis at admission including treatment offered, length of hospitalization and management.

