- (c) At delivery data to be collected will include gestational age at admission, vital signs, indication for delivery, type of delivery, compliance with protocol, blood for CBC, LFT, and the biomarkers of interest. Post-delivery, discharge vitals, antihypertensive treatment on discharge will be collected.

(d) Exit interview: patient will be called to check for any relevant ADR.

8. Data Management and Analysis plan

Data management:

Upon randomization, research coordinators will be responsible for data collection using approved CRFs. To maintain patient confidentiality, study document such as signed informed consent, and CRFs will be stored in locked cabinets, excel file containing patient identifiable information will be password protected, and all data including patient clinical information and research laboratory results will be entered into the clinical trial management software using patient generated study ID number.

Data analysis:

Descriptive data: Numerical data will be presented as mean and standard deviation where normally distributed or median and range where it's not normally distributed. Categorical data will be presented as frequency and percentages. The percentage of women developed PET will be compared between the intervention and control group using chi square test.

Quantitative data between two arms will be analyzed using either "Unpaired t test or Mann Whitney U test depending on normality of the data distribution". Also, outcomes measured at different time points should be statistically analyzed both within and between groups using repeated measure ANOVA statistical method followed by appropriate multiple comparison tests. All P values presented will be two-tailed. A multivariate logistic regression will be employed to assess the association between metformin use and PET adjusting for confounding factors such as patient demographics (age, GA at delivery, history of risk factors of PET\mentioned above) and co-morbidities such as DM, the dose of metformin, the need to use of antihypertensive drugs, including duration of treatment and any other medications. P values <0.05 will be considered as statistically significant. All Statistical analyses will be done using statistical packages SPSS 22.0 (SPSS Inc. Chicago, IL) and Epi-info (Centers for Disease Control and Prevention, Atlanta, GA) software.

9. Anticipated results and evaluation criteria

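### Control women who start metformin for gestational diabetes are moved to the intervention group for analysis, which contradicts the stated intention-to-treat analysis of pre-eclampsia

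*SAP*

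**What the plan says.** Section 5 (Study design and methodology) states that "the data will be analyzed on an intention to treat basis".

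Later in section 5, under Randomization and initiation of the study, the SAP gives a rule for crossover. When a control woman develops GDM and is put on metformin, "she will be moved to intervention group and analyzed as late started". Late start is defined nowhere. There is no matching rule for intervention women who develop GDM.

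Section 8 (Data analysis) names one between-arm test for the incidence of pre-eclampsia: "The percentage of women developed PET will be compared between the intervention and control group using chi square test". It does not say that these groups are the ones assigned at randomisation. It also does not confine the late-start rule to a secondary analysis.

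Two nearby sentences bear on the same principle. In section 5, if a woman "dropped out from the study, all her data will be removed". In section 8, a logistic regression is to "assess the association between metformin use and PET adjusting for confounding factors", and those factors include the metformin dose.

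**The concern.** Intention to treat keeps each woman in the arm she was randomised to, whatever she later receives. The crossover rule reclassifies her on two post-randomisation events, a GDM diagnosis and the start of metformin, and only if she was assigned to control. Early GDM is an exclusion criterion, so the trigger arises after entry. A moved woman must have stayed in follow-up until then, and if she is pooled with the intervention arm, her time without metformin counts as treated.

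Crossover is foreseeable. The background says metformin is often prescribed for GDM poorly controlled on diet, and section 4 describes it as first-line there under the national guideline.

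At stake is the main result: pre-eclampsia incidence is Aim 1 and the basis of the sample size. If moved women differ in risk from other controls, the test is biased even when metformin does nothing. The trial is open label, so leaving open who counts as a control also allows that choice to be made after outcomes are known.

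**Working it through.** **Inputs from the SAP.** Pre-eclampsia risk "3% versus 11.3% respectively" (metformin, control), 172 women per arm at 1:1, 80% power and 5% significance (section 6); two-tailed tests (section 8).

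**Plan's own figure.** The two-proportion formula at 11.3% versus 3%, two-sided 5%, 80% power, gives 151 per arm without continuity correction and 174 with it. The stated 172 is therefore reproduced closely by the corrected version. With 172 per arm, the uncorrected test has 85% power, which is the reference below.

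**Assumed, because the SAP gives no figure.** g is the share of controls moved (5%, 10%, 20%). r is the pre-eclampsia risk of moved women relative to other controls (0.5 to 2). *late* is the factor by which late metformin multiplies their risk.

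**Formulas.**
- Risk in unmoved controls: q0 = 0.113 / (1 + g(r − 1)).
- Risk in moved women: qg = r × q0 × late.
- Pooled reading: control has risk q0 in 172(1 − g) women; intervention has risk (172 × pI + 172g × qg) / (172 + 172g).
- Separate-group reading: pI in 172 women versus q0 in 172(1 − g).
- Rejection probability: normal approximation with pooled variance under the null, two-sided 5%, no continuity correction.

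**Worked case: no metformin effect, g = 20%, r = 2, pooled.** q0 = 0.113/1.2 = 0.0942 and qg = 0.1883. Control is 137.6 women at 9.4%. Intervention is (172 × 0.113 + 34.4 × 0.1883)/206.4 = 0.1256 in 206.4 women. The apparent relative risk is 0.1256/0.0942 = 1.33. With d = 0.0314, null standard error 0.0348 and actual standard error 0.0339:
- false harm: 1 − Φ((1.96 × 0.0348 − 0.0314)/0.0339), about 13.8%;
- false benefit: Φ((−1.96 × 0.0348 − 0.0314)/0.0339), about 0.2%;
- total: 14.0%.

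**No true effect (11.3% in both arms), r from 0.5 to 2.**

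| Reading | g | Apparent RR | Type I error at r = 0.5 | at r = 2 |
|---|---|---|---|---|
| Pooled | 5% | 0.95 to 1.10 | 5.3% | 6.0% |
| Pooled | 10% | 0.91 to 1.18 | 6.2% | 8.3% |
| Pooled | 20% | 0.83 to 1.33 | 9.6% | 14.0% |
| Separate group | 5% | 0.98 to 1.05 | 5.1% | 5.3% |
| Separate group | 20% | 0.90 to 1.20 | 6.4% | 8.1% |
| As randomised | any | 1.00 | 5.0% | 5.0% |

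At r = 1 every row gives 5%. The excess lies mainly towards false benefit when r is below 1 and towards false harm when r is above 1. A simulation of 200,000 null trials per setting at g = 20% gave 9.6% and 13.9% pooled, 6.6% and 8.1% separate, and 5.2% as randomised.

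**Allocation.** Section 5 also states "Random sized blocks of 4 or 6 will be computer generated with 1:2 ratio", against the 1:1 of section 6, without saying which arm is larger. With 344 women split 115 and 229, pooled, g = 20%, type I error is 12% to 22% if control is larger and 8% to 9% if intervention is larger.

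**True effect 3% versus 11.3%, pooled, g = 20%.** If late metformin does nothing, power is 87% at r = 0.5, 67% at r = 1 and 27% at r = 2, against 85% as randomised. If late metformin halves risk and r = 1, the move gives 80% against 77% as randomised.

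**The case against.** The best defence is that the intention-to-treat sentence covers all data without exception. On that view the groups in section 8 are the randomised ones and late start is only a descriptive label. The crossover sentence does not support this: it says she is moved and analysed on that footing, and no other text confines it. Reading it as a separate late-start group does not help either, because she still leaves control.

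Three other points have more force.
- The share moved may be small. Moved women are only those later GDM cases who are started on metformin, and nothing in the SAP supports 20%. At 5% the distortion is slight: at most 6.0% type I error if pooled and 5.3% if kept separate.
- The largest error rates, at r = 2, are almost wholly false harm, not false claims of efficacy. Under 1:1 pooling the highest rate with r below 1 is 9.6%, at r = 0.5.
- The 85% reference power is that of an uncorrected test and should not be read as the plan's 80%.

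These limit what can be said about size and direction. They do not remove the contradiction. Drop-out data and the regression exposure are secondary matters on which the finding does not depend.

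**Conclusion.** The point holds and must be fixed. The SAP gives two incompatible instructions for the same women, and followed as written the crossover rule makes the pre-eclampsia test compare groups formed partly after randomisation. That conclusion needs no assumed figure.

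The size does need assumptions. Under no true effect, bias is nil only if moved women carry the same risk as other controls. Otherwise type I error exceeds 5%, from barely (5% moved) to roughly two to three times nominal (20% moved, pooled, 1:1). Neither the direction of bias nor a loss of power can be asserted in advance, since power may fall or rise. The objection is to lost validity.

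**What to change.** Delete the move for analysis and state instead: *All randomised women are analysed in their assigned arm. Controls given metformin for GDM remain controls in the main pre-eclampsia comparison, with start date and indication recorded. Any late-start or treatment-received analysis is a labelled sensitivity analysis.* In section 8, define the chi-square groups as those assigned.

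Reconcile two other places with this rule. For drop-outs, say whether data up to drop-out are kept as far as consent allows, and report the number removed per arm. For the regression, use assigned arm as exposure in the main model, or label the model treatment-received.

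The cost is a few sentences in sections 5 and 8 and two recorded items for controls who start metformin. No extra patients are needed and GDM care is unaffected. The price is dilution if late metformin works: at g = 20% with a halving effect, and r from 0.5 to 2, the intention-to-treat relative risk is 0.28 to 0.32 instead of 0.27 (0.03/0.113), and power is about 81% to 70% instead of 85%.

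### Deleting all data of randomised women who drop out contradicts the intention-to-treat analysis; at the plan's own 20% allowance this is up to about 83 of 414 women

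*SAP*

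**What the plan says.** - **Analysis principle** (SAP section 5, Study design and methodology): "the data will be analyzed on an intention to treat basis". The same paragraph makes the trial open label, without placebo.
- **Dropout** (section 5, Randomization and initiation of the study): "If patient declined to participate initially, or dropped out from the study, all her data will be removed".
- **Order of consent and allocation.** Patient identification and randomization has the investigator "obtain informed consent once all her questions have been answered", and allocation follows successful screening. Randomization and initiation of the study says that, once a woman is recruited, "the patient data will be entered onto a web-based randomization software to determine study group". Its next sentence begins: "If the patient agrees to enter the trial, the site coordinator will contact the study physician".
- **Dropout allowance** (section 6): "Allowing for a maximum 20% dropout", 414 women are to be randomised, 207 per group.
- **What is recorded before a woman might leave.** Section 7 collects baseline data, and PET data at admission if PET occurs before the third visit. The adherence and ADR paragraph of section 5 sends adverse drug reactions "to both DSMC and MRC when they occur".
- **Main comparison** (section 8): the percentage with PET in each group, by chi-square test.

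**The concern.** Intention to treat keeps every randomised woman in her assigned arm. The deletion sentence takes out her whole record because of something that happens after randomisation. Two analysts following this document could arrive at different analysis sets, and deletion may be irreversible.

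Three things are at stake:

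- **The randomised comparison.** Only one arm is assigned metformin, treatment is open, and section 4 lists gastrointestinal side effects of metformin. Dropout may therefore differ between arms in number or in PET risk. A comparison of those who stayed could then be biased in either direction.
- **The means of checking it.** Baseline data and events already observed are what a missing-outcome sensitivity analysis would use.
- **Safety.** Reactions already reported would remain known to the DSMC and MRC but would disappear from the trial dataset. Section 9 names safety of the intervention as an evaluation criterion.

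Two terms are also loose. Dropping out is not defined: it could mean withdrawal of consent only, or also stopping tablets or missing visits. It is also unclear whether a woman who declines initially could already have been allocated.

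**Working it through.** **1. Can the two rules coexist?** Group is assigned once a woman is recruited, so a later dropout is a randomised woman. One rule includes her and the other removes her. No passage limits the removal to women who withdraw consent for use of their data, and none keeps what was collected earlier.

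**2. The plan's own numbers (section 6).** With 3% versus 11.3% PET, 80% power and two-sided 5%, the continuity-corrected formula gives 174 per arm, close to the stated 172 (151 without the correction). Inflation: 172 × 1.2 = 206.4, rounded up to 207; 2 × 207 = 414, as stated. Multiplying by 1.2 instead of dividing by 0.8 is a separate matter.

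**3. Women who could be removed.** 0.20 × 414 = 82.8, about 83, leaving about 331. The total does not depend on the allocation ratio. Expected PET cases at the planning rates are 207 × 0.113 + 207 × 0.03 = 29.6, about 30. Possible removals are thus nearly three times the expected events.

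**4. Illustration of bias, on assumed inputs.** The SAP gives no dropout by arm and no PET risk in dropouts. Assume no true effect, 11.3% PET in both arms, dropout fraction d, and dropouts at m times the completers' risk (same m in both arms). Then

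completer risk = 0.113 / (1 + d(m − 1)).

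With d = 0.20 on metformin and 0.05 in control:

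| m | Metformin | Control | RR |
|---|---|---|---|
| 0.5 | 0.1256 | 0.1159 | 1.083 |
| 1 | 0.1130 | 0.1130 | 1.00 |
| 2 | 0.0942 | 0.1076 | 0.875 |
| 3 | 0.0807 | 0.1027 | 0.786 |

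The result depends strongly on the assumed gap in dropout. With metformin at 20% and 207 per arm, using the two-sided pooled z test (equal to the uncorrected chi-square) on the remaining women:

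| Control dropout | RR, m = 2 / 3 | Type I error, m = 2 / 3 |
|---|---|---|
| 5% | 0.875 / 0.786 | 6.9% / 10.9% |
| 10% | 0.92 / 0.86 | 5.8% / 7.2% |
| 15% | 0.96 / 0.93 | 5.2% / 5.5% |
| 20% | 1.00 / 1.00 | 5.0% / 5.0% |

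Section 5 gives a different allocation from section 6: "Random sized blocks of 4 or 6 will be computer generated with 1:2 ratio". The RRs do not depend on it. For 20% versus 5% dropout, type I error at m = 2 / 3 is 6.2% / 9.0% with 138 on metformin and 276 in control, and 7.3% / 11.5% with 276 and 138.

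In this model there is no bias if dropout is unrelated to PET risk (m = 1) or if dropout is equal in both arms.

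**The case against.** - **The illustration measures informative dropout, not deletion.** A woman who leaves before PET develops has no trial outcome whether or not her earlier data are kept. This stands. Deletion itself adds the loss of baseline data, reactions and PET already recorded, and that loss is not quantified. The figures show what follow-up through the medical record could reduce, as far as consent allows it.
- **The assumed 20% versus 5% is an unfavourable corner.** This also stands, which is why the narrower gaps are shown above. The case does not rest on these figures.
- **The 83 is a planning allowance.** Agreed. Actual dropout could exceed it, and fewer women are affected if only consent withdrawal is meant.
- **Stopping tablets is an unlikely meaning of dropping out.** Adherence is measured at every visit, which presupposes that poorly adherent women stay. That is a fair reading, and leaving the study is the more natural one. Even so, it is a randomised woman who is removed, so the conflict remains.
- **The consent-order point is minor.** Screening and enrollment also ends with written consent, and the later phrase may simply be loose. That is plausible; one clarifying sentence settles it.
- **Oversight sees the reactions anyway.** It does, but the trial's own safety analysis would not include them.

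None of this removes the contradiction or supplies a rule that reconciles the two statements.

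**Conclusion.** The concern holds, and the text must be changed. The SAP states intention to treat and also a rule that removes randomised women from the dataset, including any PET already recorded for them. The rule decides who enters the main comparison. Up to about 83 of 414 women are affected at the plan's 20% maximum, taking dropout in its widest sense. The size and direction of any resulting bias are unknown and it may be zero. The RRs and type I errors above depend on assumed dropout rates and risk multipliers. The conclusion rests on the contradiction itself.

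**What to change.** Replace the deletion sentence with wording such as:

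> Data collected up to withdrawal are kept and analysed in the randomised arm. Stopping study medication is not dropout. Where the woman's consent allows, PET and delivery outcomes after withdrawal are taken from the medical record. Data are deleted only on her explicit request or where the consent already given requires it, and deletions are counted by arm.

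In section 8, state that all randomised women are analysed as assigned, and add a missing-outcome sensitivity analysis. In Randomization and initiation of the study, state that consent precedes allocation, so that women who decline initially are never randomised. Any woman already allocated when she declines is counted by arm.

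The cost is small: SAP wording, record look-up where consent permits, and a check of the consent form (appendix 4, not available here). If that form promises deletion, women already enrolled remain under that promise and are counted by arm.

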Aim 2: To determine accuracy of the ratio of PIGF/sFlt-1 in predicting PET and the effect of metformin on this ratio

The objectives under this aim will include,

1. A comparison of the serum levels of the PIGF/sFlt-1 ratio measured in early pregnancy between non-PET and PET patients.
2. A comparison of the PIGF/sFlt-1 ratio PET in patients who received metformin versus standard care group.

Aim 3: To study the molecular mechanisms and signaling pathways associated with increased levels of sFlt-1 and PET.

Regarding aim 3: in response to the reviewer's comments, the study team has agreed to collect the blood sample and placenta from the patients and store them for future analysis.

4. Preliminary data or studies

Metformin safety in pregnancy

substantial evidence on the benefits of metformin an antihyperglycemic agent when pregnant women with gestational and Type 2 diabetes. In polycystic ovary syndrome

1 Jan - Revised On May 2017

Page 5 of 22

(PCOS) patients, it is known to decrease the risk of first trimester miscarriages and the incidence of gestational diabetes (48,49). In diabetic pregnancies, metformin has been associated with favorable maternal and neonatal outcomes (50,51). Observed maternal outcomes include less weight gain during pregnancy, better glycemic control, and reduced fat distribution (52). Other benefits include a reduction in pregnancy induced hypertension and PET, lower risk of neonatal hypoglycemia and ICU admission. Neonatal outcomes include: reduced fat around organs, which could result in improved insulin resistance and prevention of diabetes later in life (52). Even though metformin is known to cross the placenta, its use in early pregnancy or late pregnancy has not been shown to be associated with an increased risk of congenital malformation or adverse neonatal outcomes except a lower neonatal birth weight (53–56).

Metformin has been safely administered at the dose we propose to use here to diabetic patients. It has become the first line treatment of type 2 DM in pregnancy and poorly controlled gestational diabetes on diet based on the NICE guideline and the national diabetes guideline in Qatar. However, anticipated side effects include: GI disturbances such as gas (4-12%), heartburn, stomach pain (3-4%), nausea (7-9%), and GI changes. Serious side effects associated with its use are hypoglycemia and lactic acidosis which are extremely rare (<1%) (57).

Metformin in PET:

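### Intention to treat conflicts with moving controls who start metformin to the intervention group; once women are analysed as randomised, the stated 80% power has no allowance for that crossover

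*SAP*

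**What the plan says.** Section 6 takes its two rates from a trial in obese women without diabetes: "metformin use was associated with 76% reduction in PET (3% versus 11.3% respectively". It sets the target with the words "We expect that for a study power of 80% and to detect a reduction at a level of 5% significance". From these it derives "172 patients in each arm, for a total of 344 in both group based on 1:1 ratio" and raises the total to 414 (207 per arm) for up to 20% dropout. No other allowance is made.

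Section 5 opens with the analysis principle: "the data will be analyzed on an intention to treat basis". Under 'Randomization and initiation of the study', the same section provides for a particular event: "In cases where patient assigned to control group and diagnosed with GDM and started on metformin". The rule is that such a woman goes to the intervention group and is analysed as a late start. The same paragraph says that the data of women who drop out will be removed.

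Section 4 gives metformin's local standing: "It has become the first line treatment of type 2 DM in pregnancy and poorly controlled gestational diabetes on diet". Section 8 compares the percentage with pre-eclampsia between arms by chi-square test, without saying whether a continuity correction is used, and adds: "All P values presented will be two-tailed".

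**The concern.** The plan gives two incompatible instructions for the same women. Intention to treat keeps them in the control arm. The Section 5 rule takes them out, so the groups compared are no longer those formed by randomisation, and membership depends on a diagnosis made afterwards.

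Settling this in favour of intention to treat is right, but it exposes a second gap. Controls who take metformin may gain some of its benefit, which brings the control rate closer to the metformin rate. Inflating for dropout replaces women whose data are lost; it does not restore a narrowed difference.

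Crossover is a realistic prospect here. The trial is open label. Section 5 excludes women with type 1 or 2 diabetes or early gestational diabetes, so later gestational diabetes will arise during follow-up. Obesity and age 35 or older both count towards eligibility.

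At stake is how a null result is read. Sections 9 and 11 say that this trial will inform a larger one. A non-significant result reported as having 80% power could be taken as lack of effect when part of the cause was metformin use in both arms.

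**Working it through.** **Inputs.** Control rate 11.3%, metformin rate 3%, power 80%, significance level 5%, 1:1 allocation, 172 per arm (all Section 6); two-sided (Section 8). The crossover rate and the effect of a late start are not in the document and are assumed below.

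**1. Reproduce the plan's figure.** Mean rate = (0.113 + 0.03)/2 = 0.0715. The usual two-proportion formula gives

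n = [1.96√(2 × 0.0715 × 0.9285) + 0.842√(0.113 × 0.887 + 0.03 × 0.97)]² / 0.083² = 150.1, so 151 per arm.

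With continuity correction: (150.1/4) × [1 + √(1 + 4/(150.1 × 0.083))]² = 173.4, so 174 per arm. The stated 172 therefore corresponds to the corrected formula with the full 8.3-point difference, and nothing is held back for crossover. Dropout: 172 × 1.2 = 206.4, rounded up to 207. Losing 20% of 207 leaves 207 × 0.8 = 165.6, about 166.

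**2. Model for intention to treat.** Let c be the share of controls who start metformin and f the share of the full benefit that they gain. Assume that they otherwise have the average control risk. Then

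control rate = 11.3% − c × f × 8.3%, with the metformin rate held at 3%.

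Example: c = 20%, f = 1 gives 11.3 − 0.2 × 8.3 = 9.64%.

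**3. Exact power**, summing binomial probabilities over all 2×2 tables with two-sided 0.05. Entries are uncorrected / continuity-corrected chi-square, in %.

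| Analysed per arm | Benefit in crossovers | 0% cross over | 10% | 20% | 30% |
|---|---|---|---|---|---|
| 172 | full | 87.4 / 82.4 | 81.3 / 75.1 | 73.6 / 66.1 | 64.1 / 55.6 |
| 172 | half | 87.4 / 82.4 | 84.6 / 79.0 | 81.3 / 75.1 | 77.7 / 70.8 |
| 172 | quarter | 87.4 / 82.4 | 86.0 / 80.8 | 84.6 / 79.0 | 83.0 / 77.1 |
| 166 | full | 86.0 / 80.8 | 79.8 / 73.3 | 71.9 / 64.1 | 62.5 / 53.6 |
| 207 | full | 92.5 / 89.8 | 87.9 / 83.9 | 81.2 / 75.9 | 72.3 / 65.7 |
| 207 | half | 92.5 / 89.8 | 90.4 / 87.1 | 87.9 / 83.9 | 84.8 / 80.2 |

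**4. The regrouping rule instead.** With 10% crossover from 172 per arm, 17.2 controls move, leaving 154.8 controls at 11.3% against 189.2 in the intervention group. If late starters gain the full benefit, the intervention rate stays at 3%. If they gain none, it is (172 × 3% + 17.2 × 11.3%)/189.2 = 3.75%. By normal approximation, power is 85.3 / 80.1 in the first case and 76.3 / 69.6 in the second; with no crossover the same approximation gives 85.1 / 79.6. The rule does not reliably protect power, and it gives up the randomised comparison.

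**The case against.** The strongest reply is that the loss is conditional. Section 5 describes a contingency and gives no frequency. The plan's own reasoning points to a small late-start effect: Section 4 attributes another trial's null result to metformin being introduced later in pregnancy, and the background calls early pregnancy the time of greatest impact. With a quarter of the benefit, the uncorrected test stays above 80% even at 30% crossover. With all 207 per arm analysed and half the benefit, both tests do. Nor can one tell from the document whether the 11.3% placebo rate already includes some open-label metformin use. All of this stands, and it argues for a table rather than a larger trial.

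Three stronger readings may tempt a reader, and the document supports none of them.

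- That the trial will have less than 80% power. This depends on the crossover rate, the late-start effect, the test variant and the number analysed, none of which the plan fixes.
- That the analysis as written dilutes the control arm. The only specific rule for these women moves them out of it; dilution follows only once intention to treat is applied.
- That 20% of the metformin arm will stop the drug, diluting the effect from the other side. The 20% is dropout, with data removed. The 3% was observed in women assigned to metformin and may already include some who stopped.

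**Conclusion.** The contradiction within Section 5 is definite and should be resolved by analysing every woman as randomised. Given that, the 80% in Section 6 is a no-crossover figure, and the plan does not say so. How much power is lost is unknown. At 172 per arm, 10% to 30% crossover with full benefit gives 81% down to 64% uncorrected, or 75% down to 56% corrected. At the 166 per arm left after the plan's dropout, 10% crossover gives 79.8 / 73.3%. The loss is small if late metformin does little, and 10% crossover leaves more than 80% if all 207 per arm are analysed.

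These figures assume 1:1 allocation as in Section 6, the rates of 11.3% and 3%, and crossovers of average risk. They concern the analysis and the stated power only, not how gestational diabetes is treated.

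**What to change.** Keep the planned enrolment.

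- In Section 5, remove the late-start regrouping from the primary comparison and state that each woman is analysed in her randomised arm whatever she later takes.
- In Section 6, state that 80% assumes no control crossover. Add a short table of intention-to-treat power by crossover rate (for example 0, 10, 20 and 30%) and late-start effect (full, half, quarter). Name the chi-square variant and the number analysed. The site's own records of metformin use for gestational diabetes could indicate which column is realistic.
- Report the number of controls who started metformin beside the pre-eclampsia result.
- A complier-average analysis, with randomised arm as the instrument, may be added as a supplement but is optional.

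The cost is some wording, one small table and one reported count, with no extra patients or procedures. The downside is a less favourable stated power.
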